### 9.3 POPULATIONS FOR ANALYSES

The following datasets will be used for analysis:

1. Intention-to-Treat (ITT) Analysis Dataset (i.e., all randomized participants)
2. Per-Protocol Analysis Dataset: defines a subset of the participants in the full analysis set who complied with the protocol sufficiently to ensure that these data would be likely to represent the effects of study intervention according to the underlying scientific model.
3. Pre-specified subgroup analyses – (1) Gender, (2) decade of age, (3) pattern of AF, (4) warfarin naïve vs prior warfarin exposure, (5) Time in therapeutic range on warfarin divided by the median.

### 9.4 STATISTICAL ANALYSES

#### 9.4.1 GENERAL APPROACH

Continuous and categorical variables will be summarized as mean (standard deviation, SD) and number (%) respectively. Differences between the two treatment arms at baseline will be examined using t-tests for continuous variables and chi-square tests for categorical variables.

The baseline variables include age, sex, education, cardiovascular risk factors (hypertension, diabetes mellitus, hyperlipidemia), past medical history (including stroke, TIA, heart failure, peripheral arterial disease, MI, coronary artery disease, liver disease, renal disease, malignancy), duration of AF, pattern of AF (paroxysmal, persistent), prior h/o anticoagulation (duration and type of drug used), prior treatment of AF (antiarrhythmic drug, ablation procedure), and current medications. This data will be reviewed and updated at each visit. The INR values during the study will be collected for patients on warfarin and the time in therapeutic range calculated using the Rosendaal method of interpolation.

Longitudinal changes in each cognitive domain (language, attention, memory, visual spatial and global) will be analyzed using multiple adjusted linear mixed effects models comparing Apixaban vs warfarin. These models will be adjusted for baseline variables that differ between the groups. These results will be presented as beta estimates for baseline differences in cognitive function score by treatment status, change with time and the effect of treatment on the change in scores over time.

For the secondary end point of dementia/MCI, the mid-point between the most recent visit with a cognitively normal diagnosis and the first visit with a diagnosis of MCI or dementia will be considered the date of onset. Participants who are lost to follow-up or die during follow-up will be censored at the

date of last follow-up. Cox proportional hazards model will be used to assess the secondary end points of MCI/dementia, cerebral infarction and cerebral microbleeds. Adjustment for baseline factors noted above will be performed in the multivariable model.

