#### *Mechanisms Underlying the Association between Atrial Fibrillation and Dementia*

The mechanisms for the association between AF and cognitive decline are intricate and multifactorial. Potential mechanisms include linking atrial fibrillation and cognitive impairment/dementia include

cerebral hypoperfusion, vascular inflammation, cerebral vascular disease, thromboembolism and brain atrophy. Of particular interest and felt to play a major role is cerebral infarction, both overt and subclinical.

Cerebral infarctions occur due to systemic embolism as a consequence of AF and are associated with significant risk of dementia in the general population and in patients with AF. While overt stroke is one of the most feared sequela of AF, subclinical cerebral ischemic lesions (as detected by magnetic resonance imaging [MRI]) have been reported in up to 90% of participants with AF. These lesions have been consistently associated with an increased rate of dementia and decline in global cognitive function.

Similarly, CMBs also contribute towards the association of AF and dementia or cognitive decline. CMBs are asymptomatic cerebral hemorrhages detected by MRI that often occur in association with cerebral amyloid angiopathy. They increase the risk for intracranial hemorrhage (particular in the setting of anticoagulation for AF and are associated with worse cognitive outcomes. Remarkably, in AF patients that manifest cognitive impairment, there is often a significant presence of cerebral micro bleeds detected on brain MRI in patients.

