To assess the development of mild cognitive impairment or dementia	
Clinical dementia rating scale
 
Dementia Subjects with a CDR 1 will be classified as demented if they meet DSM-V criteria for ‘major neurocognitive disorder’ as follows:
 
 
1. Evidence of significant cognitive decline from a previous level of performance in one or more cognitive domains based on:               
 
a. Concern of the individual, a knowledgeable informant, or the clinician that there has been a significant decline in cognitive function; and
 
b. A substantial impairment in cognitive performance, preferably documented by standardized neuropsychological testing.
 
 
 
2. The cognitive deficits interfere with independence in everyday activities.
 
3. The cognitive deficits do not occur exclusively in the context of delirium and are not better explained by another mental disorder.
 
 
For subjects with CDR 0.5, a committee of the examining
	The development of dementia or mild cognitive impairment are important end points with clinical relevance to the patient.

OBJECTIVES	ENDPOINTS	JUSTIFICATION FOR ENDPOINTS
	
neuropsychologist and physician will critically examine the available tests to determine whether the DSM-V criteria for dementia or MCI are met.
 
Mild cognitive impairment                      The criteria for diagnosis of MCI are: cognitive concern expressed by a physician, informant, participant or nurse; cognitive impairment in 1 or more domains; normal functional activities and not demented. Subjects with MCI can have a CDR of 0 or 0.5; however, the final diagnosis of MCI will not be based exclusively on the CDR but rather on all available data. A committee of the examining neuropsychologist and physician will critically examine the available tests to determine whether the criteria for MCI are met.
	
Tertiary end points		
MRI detected new cerebral ischemic lesions and cerebral microbleeds (CMBs)	Brain MRI will be performed at baseline and 2 years to assess the presence of new cerebral ischemic lesions on DTI imaging and new cerebral microbleeds on SWAN sequences.	The presence of cerebral infarcts, even clinically silent ones, have been associated with higher future risk of dementia. Similarly, CMBs are associated with dementia and future risk for intracerebral hemorrhage.

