## 4 STUDY DESIGN

### 4.1 OVERALL DESIGN AND SCIENTIFIC RATIONALE FOR STUDY DESIGN

Our primary hypothesis is that in patients with atrial fibrillation, anticoagulation with Apixaban reduces the rate of decline in cognitive function, when compared to Warfarin. We also hypothesize that Apixaban reduces cognitive decline by reducing the rate of new cerebral infarction and cerebral microbleeds detected by cerebral MRI compared to warfarin.

This is a phase 3, open-label, single site, randomized control trial comparing neuropsychological and neuroimaging outcomes in AF patients randomized to Apixaban vs Warfarin. Patients over the age of 60 y with ECG documentation of NVAf in patient records and CHA2DS2-VaSC score ≥2, eligible for oral

anticoagulation will be randomized to Apixaban or dose adjusted warfarin (target INR 2 – 3) for a period of 2 years. Randomization will be stratified by decade of age, and gender. All patients will undergo neuropsychometric testing at baseline, 1 and 2 years and brain MRI at baseline and 2 years. Study personnel performing and interpreting the neuropsychometric tests and brain MRI will be blinded to treatment allocation.

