### **Brain MRI imaging to assess burden of cerebral infarcts and cerebral microbleeds**

#### **MR Imaging of brain**

Cerebral MRI will be performed *without* gadolinium contrast using a 3 Tesla scanner at enrollment and at 2 years. If a subject is withdrawn or withdraws prior to the completion of follow-up, an attempt to obtain MRI prior to withdrawal will be made. The following imaging sequences will be performed per standard protocols at our institution: (1) sagittal T1-weighted, (2) axial T2-weighted fast spin echo (FSE), (3) axial T2-weighted fluid-attenuated inversion recovery (FLAIR), (4) axial gradient echo (GRE), (5) axial diffusion tensor-tracer imaging (DTI), (7) 3-dimensional magnetization prepared rapid gradient-echo (MPRAGE) sequence and (8) Axial SWAN (T2 Star Weighted Angiography).

The MRI will be read by a board certified Radiologist who is blinded to treatment assignment.

A new cerebral infarct will be defined as an unequivocal focus of hyperintensity to gray matter on DTI images. GRE and MPRAGE sequences will be used to quantitate the cerebral microbleeds. Cerebral volume analysis will be performed for total cerebral and hippocampal volume using standardized software. The number, size and location of new cerebral infarcts (cortical vs. subcortical and specific anatomic location of infarct) and cerebral microbleeds (lobar vs subhemispheric and specific anatomic location of infarct) will be determined and documented in a CRF.

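### The secondary models in Section 9.4.1 adjust for a long clinical list but not for the baseline measure of each outcome

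*Combined protocol and SAP*

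**What the plan says.** Section 9.4.1 names one model type for all three outcomes: "Cox proportional hazards model will be used to assess the secondary end points of MCI/dementia, cerebral infarction and cerebral microbleeds". The covariates follow: "Adjustment for baseline factors noted above will be performed in the multivariable model". The factors meant are those listed earlier in the same section. That list opens with "The baseline variables include age, sex, education, cardiovascular risk factors (hypertension, diabetes mellitus, hyperlipidemia), past medical history", goes on through AF duration and pattern and anticoagulation history, and closes with "prior treatment of AF (antiarrhythmic drug, ablation procedure), and current medications". It names no MRI finding and no cognitive score, and no other section adds one.

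Both measures are collected. Section 4.1 states: "All patients will undergo neuropsychometric testing at baseline, 1 and 2 years and brain MRI at baseline and 2 years". Section 8.1 has the MRI done "using a 3 Tesla scanner at enrollment and at 2 years" and requires the baseline scan before study drug. Cognition may be tested up to a month after enrollment (Section 8.1) or randomization (Section 3).

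Randomization is stratified by decade of age and gender only (Sections 4.1 and 6.1.1). Section 5.2 excludes dementia at entry but not MCI.

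**The concern.** A patient's state at entry is a natural covariate for a later change in that state. MCI is defined partly by impairment in at least one cognitive domain, so a patient who starts near that threshold is closer to the event. For the MRI outcomes, Section 3 says: "Brain MRI will be performed at baseline and 2 years to assess the presence of new cerebral ischemic lesions on DTI imaging". The baseline scan is therefore already the reference for calling a lesion new, but it is not used as a covariate.

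Two things are at stake. First, with about 140 patients per arm and no stratification on these factors, the arms can differ by chance in baseline lesions or cognition, and the named covariates do not directly correct for that. Second, in a proportional-hazards or logistic model, leaving out a strong predictor moves the estimated treatment effect toward no effect and lowers power.

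**Working it through.** **The plan's own figure.** No power, event rate or hazard ratio is stated for the secondary endpoints. The stated size is for the primary slope (Section 9.2: difference 0.05/year, SD 0.16, 140 per arm, one-sided 0.05):

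- z = 0.05 / (0.16 × √(2/140)) = 2.61, and power = Φ(2.61 − 1.645) ≈ 83%, which agrees with the stated >80%.
- 140 / 0.8 = 175 per arm, as stated.

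The present point changes neither figure.

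**Power with and without one baseline predictor.** MRI is taken only at baseline and 2 years, so a grouped proportional-hazards model (complementary log-log) was simulated, with 2,000 trials per scenario. Taken from the plan: 140 per arm. Assumed: true HR 0.5, two-sided 5%, complete follow-up, no other covariates, and the control-arm 2-year rates and predictor strengths shown. Entries are power without → with the predictor.

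| Baseline predictor | Rate 10% | Rate 20% | Rate 30% |
|---|---|---|---|
| Present in 30%, HR 2 | 32 → 32% | 58 → 59% | 76 → 77% |
| Present in 30%, HR 3 | 30 → 31% | 58 → 60% | 75 → 78% |
| Present in 30%, HR 5 | 29 → 31% | 54 → 58% | 69 → 77% |
| Continuous, HR 2 per SD | 29 → 30% | 54 → 58% | 72 → 78% |
| Continuous, HR 3 per SD | 28 → 32% | 48 → 59% | 63 → 77% |

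The gain runs from about 0 to 14 points. Without the predictor, the median estimated HR reaches at most 0.56 for a true 0.50.

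**Sensitivity to lesion prevalence.** Section 2.2 says subclinical ischemic lesions "have been reported in up to 90% of participants with AF". A logistic version (140 per arm, 3,000 trials, all rates assumed) gives, for 2-year risk with v without a baseline lesion:

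- 90% prevalence, OR 0.5: risk 20% v 10%, power 51.6 → 51.9%; 30% v 10%, 64.5 → 65.2%; 50% v 10%, 75.9 → 78.1%.
- 25% prevalence, risk 20% v 5%: 25.1 → 25.6%.
- 25% prevalence, risk 50% v 10%, OR 0.5: 40.5 → 47.2%.
- 30% prevalence, risk 60% v 10%, OR 0.45: 50.8 → 63.2%.

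Yes/no lesion presence adds almost nothing when nearly everyone has a lesion. The larger gains need a strong predictor at moderate prevalence.

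**Chance imbalance.** At an assumed 30% prevalence, the 95% range of the between-arm difference is ±1.96 × √(2 × 0.3 × 0.7 / 140) = ±10.7 points, that is, 35.4% v 24.6%. For a low event rate and predictor hazard ratio k, the apparent HR with no treatment effect is about (1 + 0.3537(k − 1)) / (1 + 0.2463(k − 1)), which gives 1.09, 1.14 and 1.22 for k = 2, 3 and 5. The exact calculation at a 20% event rate gives 1.08, 1.14 and 1.21.

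**Load of the existing list.** It holds about 21 terms before medications: age, sex, education (3); three risk factors (6); nine history items (15); AF duration and pattern (17); anticoagulation duration and type (19); antiarrhythmic drug and ablation (21). Expected events are 140r + 140(1 − (1 − r)^0.5), or about 21, 43 and 65 at r = 10%, 20% and 30%. That is about 1 to 3 events per term.

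**The case against.** - **The power comparison is not with the planned model.** It sets one covariate against none. The listed factors include age, prior stroke, TIA and hypertension, which may already carry part of the same information. This stands: the gain over the planned covariates is unknown and may be smaller than the table shows.
- **The list may be open.** It is introduced as what the variables include. This stands as a reading, but the text still does not pre-specify these covariates, and choosing them later in an open-label trial would invite dispute.
- **Baseline cognition may be measured on drug.** This stands. Section 8.1 protects only the MRI from this, so the z-score needs a sensitivity analysis.
- **The data may not be ready to use.** Section 8.1 defines and records new infarcts, not baseline infarcts, and Section 10.1.6.1 stores cognitive and clinical data in separate systems. This stands in part: a baseline count must be added to the read, but the scan exists and must be read anyway to call a later lesion new.
- **Adding terms would overload the models.** This stands against lengthening the list. It favors replacing it.

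A reader might infer that the plan throws away its strongest predictors. The documents do not support that. Section 4.1 links MRI findings to later cognitive decline, but nothing ranks or quantifies baseline lesions as predictors of new ones.

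**Conclusion.** The omission is real and worth correcting, but its effect is modest. Under the assumptions shown, adjustment adds about 0 to 14 points of power. The gain is near 0 if the predictor is weak or lesion presence is near universal. Adjustment also guards against an imbalance that, at its 95% limit, would shift the HR by about 8 to 21% for predictor HRs of 2 to 5. All rates, prevalences and predictor strengths are assumptions.

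Two stronger conclusions might be inferred, and neither follows. First, the secondary comparisons are not systematically biased: randomization holds, and the shift toward 1 applies only when there is a true effect. Second, the primary result is not at risk: the mixed model already uses the baseline score as its first repeated measure, and the sample size is unchanged. Only secondary endpoints are involved, and Section 3 labels the MRI outcomes tertiary.

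**What to change.** In Section 9.4.1, replace the sentence on adjustment for the factors listed above with a short pre-specified set per endpoint:

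- new infarcts: age decade, sex and baseline infarct count category;
- new microbleeds: age decade, sex and baseline microbleed count category;
- MCI/dementia: age decade, sex and baseline global z-score.

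Use count categories because lesion presence may be near universal. Define a baseline infarct and the count categories, and record baseline counts from the blinded read of the baseline MRI. For the z-score, use the baseline test and add a sensitivity analysis limited to patients tested before starting study drug. Because baseline MCI is allowed and onset is dated from the last cognitively normal visit, also state whether such patients are at risk for the MCI/dementia endpoint.

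The cost is a wording change, baseline count fields on the MRI form and a link between the two databases. No new visit or scan is needed. The change should be made before any outcome is compared by arm.

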## 6 STUDY INTERVENTION

### 6.1 STUDY INTERVENTION(S) ADMINISTRATION

#### 6.1.1 STUDY INTERVENTION DESCRIPTION

##### ***Study intervention***

Participants will be randomly assigned 1:1 to one of 2 treatment arms. Randomization will be stratified by decade of age and gender. Drug administration will be according to the FDA approved labeling.

*Treatment arm 1 (Apixaban arm)* will receive Apixaban 5 mg twice daily unless patient has any 2 of the following: Age  $\geq 80$  years, body weight  $\leq 60$  kg, or serum creatinine  $\geq 1.5$  mg/dL, then reduce dose to 2.5 mg twice daily.

For patients receiving a non-Apixaban anticoagulant at the time of enrollment, the following procedure will be followed to convert them to Apixaban:

Conversion from warfarin to apixaban: Discontinue warfarin and initiate apixaban when INR is <2

Conversion from other non-warfarin anticoagulants (oral or parenteral) to apixaban: Discontinue the other non-warfarin anticoagulant and begin taking apixaban at the usual time of the next scheduled dose of the other non-warfarin anticoagulant.

*Treatment arm 2 (Warfarin arm)* will receive dose adjusted warfarin to maintain INR between 2 – 3. Dose adjustment performed using a standardized nomogram at an anti-coagulation clinic will be encouraged but not required. Interval of INR testing will be determined by the treating physician.

For patients receiving a non-Apixaban oral anticoagulant at the time of enrollment, the following procedure will be followed to convert them to Warfarin: The anticoagulant will be continued until the INR is  $\geq 2$ .

For patients receiving a parenteral anticoagulant at the time of enrollment to the warfarin arm, the treating physician will determine the need for ‘bridging’ anticoagulation until the INR is therapeutic.

---

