## 9.2 SAMPLE SIZE DETERMINATION

Sample size calculation is based on the primary endpoint, the rate of decline in the global cognitive function score. The sample size calculations are based on data from the Mayo Clinic Study of Aging which has enrolled community dwelling individuals to perform the same battery of neurocognitive tests proposed in this study. We investigated the rate of decline in the global cognitive function score in (1) patients with and without AF and (2) in AF patients on warfarin vs. not on warfarin. The Mayo Clinic Study of Aging (MCSA) has identified a significant decline in the individual and global cognitive function scores in patients with AF compared to those without AF. In addition, the rate of decline was similar in AF patients treated with warfarin and those not treated with warfarin. The observed rate of decline in global cognitive score in AF patients on warfarin was -0.12 / year (SD 0.16). A reduction in the rate of decline in the global cognition function score of 0.05/year with Apixaban compared to Warfarin was considered clinically relevant. We used R to calculate power as a single sided test of superiority of Apixaban over Warfarin. A sample size of 140 in each arm is required to achieve >80% power to detect

the difference stated assuming an alpha error of 0.05. Assuming a screen failure rate of 20%, a total of 175 will be accrued in each arm.

Enrollment will be age and gender stratified with goal of enrolling >50% patients over the age of 70 years in whom the risk of cognitive decline is greater. Recruitment of the required number of subjects will be feasible given the high volume of AF patients in the local community and those seeking care for AF at the Mayo Clinic. For example, 5000 individuals developed incident (new onset) AF in Olmsted county alone after the year 2000. The rate of prevalent AF is higher in this population. The other 7 counties from which participants will be recruited have similar population demographics and prevalence of AF. We anticipate that we will be able to recruit the required number of subjects in the first year of the study.

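### The primary model takes its covariates from chance baseline differences rather than fixing the stratification factors, and the time-in-therapeutic-range subgroup exists in one arm only

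*Combined protocol and SAP*

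**What the plan says.** **Covariates.** Section 9.4.1 first screens for imbalance: "Differences between the two treatment arms at baseline will be examined using t-tests for continuous variables and chi-square tests for categorical variables". It then says of the longitudinal models for the domain and global scores: "These models will be adjusted for baseline variables that differ between the groups". It gives no threshold for a difference, no fixed list, and no statement of whether a selected covariate enters as a main effect or also by time. The reported results are to include "change with time and the effect of treatment on the change in scores over time".

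**Stratification.** Section 4.1 states "Randomization will be stratified by decade of age, and gender", and Section 6.1.1 repeats it. Section 9.2 sets a "goal of enrolling >50% patients over the age of 70 years in whom the risk of cognitive decline is greater". Nothing in Section 9 puts age decade or gender into the primary model.

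**TTR.** Item 5 of the pre-specified subgroups in Section 9.3 is "Time in therapeutic range on warfarin divided by the median". The other four are gender, age decade, AF pattern and prior warfarin exposure. Section 9.4.1 derives TTR from INRs recorded during the study in warfarin patients. Section 4.2 leaves the testing interval to the treating physician.

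**The concern.** After randomisation, any baseline difference found by testing is a chance difference. A rule that adjusts for such differences leaves the primary model open until the data are examined, in an open-label trial where the model should be settled beforehand. It also works against the design: stratified allocation balances age decade and gender, so the two factors the trial chose to control are the least likely to be selected.

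The TTR item is a different kind of problem. A subgroup analysis of a treatment effect needs a variable defined in both arms and not affected by treatment. On-study TTR meets neither condition. Section 2.2 reports roughly doubled dementia rates in patients with the poorest INR control, so the low-TTR half may differ in prognosis. A comparison with apixaban could then look like a larger benefit where warfarin is poorly controlled, and would carry the credibility of a pre-specified subgroup.

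**Working it through.** **1. The plan's own figure.** Section 9.2 gives SD 0.16, difference 0.05/year, 140 per arm, one-sided, sized to detect "the difference stated assuming an alpha error of 0.05".

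- SE = 0.16 × √(2/140) = 0.01912
- z = 0.05 / 0.01912 = 2.615
- Power = Φ(2.615 − 1.645) = 83.4%, which agrees with the stated >80%.

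**2. Value of fixing the strata.** Let R² be the share of slope variance that the strata explain. The documents give no value, so a range is shown.

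- Strata ignored: Φ((2.615 − 1.645)/√(1 − R²))
- Strata-by-time fitted: Φ(2.615/√(1 − R²) − 1.645)

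| Assumed R² | Power, strata ignored | Power, strata-by-time | Gain (points) |
|---|---|---|---|
| 0% | 83.4% | 83.4% | 0 |
| 2% | 83.6% | 84.0% | 0.4 |
| 5% | 84.0% | 85.0% | 1.0 |
| 10% | 84.7% | 86.7% | 2.0 |

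**3. What the selection rule picks.** Section 9.4.1 lists about 22 baseline variables (current medications counted as one), or 20 without age and sex. Assume the threshold is p<0.05, because the plan states none.

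- Expected number picked by chance: 20 × 0.05 = 1.0
- At least one picked: 1 − 0.95^20 = 64%, if the tests are independent
- Age or gender picked: 0 of 3000 simulated trials, with stratified blocks of 4 or of 8 (assumed; no block scheme is stated)

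**4. Effect on the treatment-by-time estimate.** Simulation of 280 patients with visits at 0, 1 and 2 years, 20 independent covariates acting on intercept and slope, selection at p<0.05, and 3000 trials per scenario.

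- Main effects only, complete data: the estimate changes by at most 1.4e-17, which is numerical zero.
- Main effects only, 20% random dropout (assumed): mean change 0.00003/year, maximum about 0.0004.
- With covariate-by-time terms, which the plan does not state: mean change 0.0023, 0.0026 and 0.0034/year at R² of 5, 10 and 20%. That is 5 to 7% of 0.05. One-sided rejection under no effect is 4.9, 4.7 and 3.8%, so there is no inflation.

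**5. TTR as a subgroup.** Three cells exist: apixaban, warfarin low TTR and warfarin high TTR. A design with intercept, treatment, TTR half and their product has 4 columns and rank 3, so the interaction has 0 degrees of freedom at any sample size.

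Suppose instead that each half is compared with all apixaban patients (comparator assumed), with no drug effect and a correlation r between TTR and slope (assumed). For a median split of a normal variable, each half shifts by r × √(2/π) × 0.16.

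| Assumed r | Shift per half (/year) | Share of 0.05 | Gap between halves (/year) |
|---|---|---|---|
| 0 | 0 | 0% | 0 |
| 0.1 | 0.013 | 26% | 0.026 |
| 0.2 | 0.026 | 51% | 0.051 |
| 0.3 | 0.038 | 77% | 0.077 |

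The low half looks worse than apixaban and the high half better, by the same amount.

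**The case against.** **The covariate rule does almost no numerical damage.** It causes no type I inflation, leaves the sample size alone, and as main effects barely moves the estimate. This stands, and the point is therefore rated modest. What remains is a primary model whose threshold and form are left open, and a small gain in precision forgone.

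**Age is already handled by norming.** Section 9.1 age- and education-adjusts the scores, so the greater risk over 70 may not carry over to slopes on the normed scale. This is fair, and it is why the R² range starts at 0. Norming does not cover gender and puts no strata term in the model.

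**The selection figures borrow a threshold.** The 0.05 is the sample-size alpha, and independence is doubtful for pairs such as stroke and TIA. This also stands: 1.0 and 64% are illustrations. That the rule tends to miss the stratification factors follows from stratification itself.

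**Section 9.3 names no comparator, so TTR could be meant as a description within warfarin.** That reading is possible, but the item sits among the subgroup analyses without distinction. At r = 0.1 the shift is also only about half a standard error (0.16 × √(1/70 + 1/140) = 0.023). Part of a TTR gradient could reflect how well warfarin was working, since Section 2.2 ties its efficacy to TTR. The trial cannot separate that from differences between patients, which is a reason not to present it as a treatment effect.

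**Conclusion.** Both parts hold. The covariate rule should be replaced, but its harm is modest: a forgone gain of 0 to 2.0 power points for assumed R² of 0 to 10%, plus avoidable discretion over the model. The estimate moves materially only if by-time terms are added for the selected covariates, which the plan neither requires nor rules out.

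The TTR item carries most of the weight. That it is post-randomisation, absent under apixaban and unable to support an interaction follows from the text and needs no assumption. The size of the possible distortion (0 to 0.038/year per half) depends on the assumed correlation and comparator. The primary test is not affected by it. This is a change the sponsor should make, not one on which the validity of the primary result depends.

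**What to change.** **Section 9.4.1.** Replace the adjustment sentence with: *The primary mixed model contains treatment, time, treatment-by-time, age decade, gender, age decade-by-time and gender-by-time. No covariate is added or removed because of observed baseline differences.* The Cox covariates can stay; at most, clarify that they are a list fixed in advance that includes age decade and gender.

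**Section 9.3.** Remove item 5 from the treatment-effect subgroups and add: *TTR will be reported descriptively within the warfarin arm as a non-randomised analysis.* Items 1 to 4 stay.

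**Cost.** Wording, and about 6 model degrees of freedom with three age decades and two genders (2 + 1 main effects, 2 + 1 by time). There is no upper age limit, so a fourth decade would make it 8 (3 + 1 and 3 + 1). Both factors are already recorded for randomisation, so no new data, patients or visits are needed.
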